10.1. Adverse Events

All new or worsening AEs occurring from the time of signing of the ICF through the end of the study will be recorded and coded using the MedDRA® dictionary. The definitions of AEs, serious adverse events (SAEs), and adverse events of special interest (AESIs) are provided in Sections 10.2.1-10.2.3 of the protocol.

Pre-treatment AEs and TEAEs are defined as follows:

- Pre-treatment AEs are AEs that developed or worsened in severity during the pre-treatment period, as defined above.
- TEAEs are AEs that developed or worsened in severity compared to baseline during the on-treatment and follow-up periods, as defined above. As only new AEs that were not present at baseline and pre-existing AEs that worsen during the on-treatment and follow-up periods will be summarized in this study, all AEs collected during the on-treatment and follow-up periods are considered TEAEs.

Adverse events will be summarized with incidence tables. Adverse event incidence tables will present the number and percentage of patients experiencing an AE within each treatment group, sorted by decreasing frequency of SOC and PT in the dupilumab treatment group. Multiple occurrences of the same event in a patient will only be counted once in the summaries. For tables showing AE severity, if a patient has multiple occurrences of the same PT or SOC, only the worst severity will be counted in the summary.

AE summaries will be presented for the TEAEs. The following summaries for TEAEs will be presented by treatment group:

- Overview of TEAEs, consisting of the number and percentage of participants with any TEAE, with any drug-related TEAE, with any TEAE leading to permanent discontinuation of study drug, with any TEAE resulting in death, with any treatment-emergent SAE, with any treatment-emergent, drug-related SAE, and with any treatment-emergent SAE leading to permanent discontinuation of study drug.
- TEAEs by primary SOC and PT
- TEAEs by primary SOC, high level term (HLT), and PT
- TEAEs by primary SOC, PT, and severity (according to the grading scale in Section 10.2.4 of the protocol)
- TEAEs by primary SOC and PT that occur in $\geq 5\%$ of patients in either treatment group
- TEAEs related to study drug by primary SOC and PT
- Injection site reaction TEAEs by primary SOC, HLT, and PT
- TEAEs with fatal outcome by primary SOC and PT
- Serious TEAEs by primary SOC and PT
- TEAEs leading to permanent discontinuation of study treatment by primary SOC and PT

10.1.1. Adverse Events of Special Interest

Adverse events of special interest for this study are as follows:

- Anaphylactic reactions
- Systemic hypersensitivity reactions
- Helminthic infections
- Any severe type of conjunctivitis or blepharitis
- Keratitis
- Clinically symptomatic eosinophilia (or eosinophilia associated with clinical symptoms)

Summaries of treatment-emergent AESIs by AESI category, primary SOC, and PT using the search criteria specified in [Table 1](#) will be presented.

Table 1: AESI Categories and Corresponding Search Criteria

AESI Category	Search Criteria
Anaphylactic reactions	Narrow SMQ for “Anaphylactic reaction”
Systemic hypersensitivity reactions (excluding events already included under anaphylactic reactions)	Narrow SMQ for “Hypersensitivity” minus narrow SMQ for “Anaphylactic reaction”, followed by blinded adjudication by the Sponsor clinical team
Helminthic infections	HLT of “Cestode infections” or “Helminthic infections NEC” or “Nematode infections” or “Trematode infections”
Any severe type of conjunctivitis or blepharitis	(Broad CMQ for “Conjunctivitis” or any PT containing “blepharitis” and with severity recorded as “Severe”
Keratitis	Narrow SMQ for “Corneal disorders”
Clinically symptomatic eosinophilia (or eosinophilia associated with clinical symptoms)	HLT of “Eosinophilic disorders” or PT of “Eosinophil count increased”, followed by blinded adjudication by the Sponsor clinical team

Note: PTs included in this table are based on MedDRA® version 26.1. If a more recent version of MedDRA® is available and is used for reporting purposes, the PTs used in the programming logic for the search criteria will be updated accordingly.

AESI=adverse event of special interest; CMQ=custom MedDRA® query; HLT=High Level Term; MedDRA®=Medical Dictionary for Regulatory Activities; NEC=not elsewhere classified; PT=preferred term; SMQ=standardized MedDRA® query.

10.2. Laboratory Parameters

Blood chemistry, hematology, urinalysis, and other laboratory testing samples (including pregnancy testing samples) will be analyzed by a central laboratory. Detailed instructions for blood sample collection are included in the laboratory manual provided to study sites.

The following laboratory tests will be collected and summarized by treatment group according to the time points specified in the Schedule of Time and Events in Section 14.2:

Blood Chemistry

- Sodium
- Potassium
- Chloride
- Carbon dioxide
- Calcium
- Glucose
- Albumin
- Total protein, serum
- Creatinine
- Blood urea nitrogen (BUN)
- Aspartate aminotransferase (AST)
- Alanine aminotransferase (ALT)
- Alkaline phosphatase (ALP)
- Lactate dehydrogenase (LDH)
- Total bilirubin
- Total cholesterol
- Triglycerides
- Uric acid
- Creatine phosphokinase (CPK)

Hematology

- Hemoglobin
- Hematocrit
- Red blood cells (RBCs)
- White blood cells (WBCs)
- Red cell indices
- Platelet count

Differential:

- Neutrophils
- Lymphocytes
- Monocytes
- Basophils
- Eosinophils

Urinalysis

- | | | |
|--------------------|----------------------|---------------------------|
| ▪ Color | ▪ Glucose | ▪ RBC |
| ▪ Clarity | ▪ Blood | ▪ Hyaline and other casts |
| ▪ pH | ▪ Bilirubin | ▪ Bacteria |
| ▪ Specific gravity | ▪ Leukocyte esterase | ▪ Epithelial cells |
| ▪ Ketones | ▪ Nitrite | ▪ Crystals |
| ▪ Protein | ▪ WBC | ▪ Yeast |

Other Laboratory Tests

Other laboratory tests include:

- Antineutrophil cytoplasmic antibodies (ANCA) at screening
- Hepatitis screen including hepatitis B surface antigen (HBsAg), hepatitis B surface antigen antibody (HbsAb), hepatitis B core antibody (HbcAb), and hepatitis C virus antibody (HCVAb)
- Human immunodeficiency virus (HIV) (anti-HIV-1 and anti-HIV-2 antibodies) serology
- Serum immunoglobulin G (IgG) against *A fumigatus*
- *A fumigatus* skin testing
- Serum *A fumigatus*-specific IgE
- Urine toxicology for drug screening
- Pregnancy test: for women of childbearing potential (WOCBP), pregnancy testing will include a serum pregnancy test at screening and urine pregnancy tests at subsequent time points as specified in the Schedule of Time and Events in Section 14.2.

All laboratory values must be reviewed by the investigator or authorized designee.

Significantly abnormal test results that occur after the start of study treatment must be repeated to confirm the nature and degree of the abnormality. When necessary, appropriate ancillary investigations should be initiated. If the abnormality fails to resolve or cannot be explained by events or conditions unrelated to the study drug or its administration, the medical/study director must be consulted.

The clinical significance of an abnormal test value, within the context of the disease under study, must be determined by the investigator.

Criteria for reporting laboratory values as an AE are provided in Section 10.1.1 of the protocol.

Clinical laboratory analytes will be converted to standard international (SI) units and grouped by function in summary tables. Clinical laboratory values and change from baseline in clinical laboratory values at all scheduled post-baseline assessment time points will be summarized via descriptive statistics by treatment group.

Patient laboratory parameter measurements will be evaluated by PCSV criteria, specifically identifying patients with at least 1 post-baseline measurement that meets the PCSV criteria (see Section 14.3). Patients meeting the PCSV criteria will be summarized by patient count (and percentage) for a post-baseline PCSV measurement by treatment group. When the PCSV definition involves a change from baseline value, patients must have a baseline value to be included in the summaries. All measurements collected during the study, including values from unscheduled visits, will be used in the PCSV analyses.

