#### 3.3.1. Risk/Benefit for Dupilumab

Dupilumab has shown clinically relevant benefit in several type 2-mediated immune disorders including AD, bronchial asthma, CRSwNP, and eosinophilic esophagitis (EoE).

In adults and adolescents with moderate-to-severe uncontrolled asthma, dupilumab significantly reduced the risk of severe exacerbations compared to placebo and consistently improved lung function (FEV1), asthma control, and HRQoL in patients with a type 2 inflammatory signature as evidenced by a blood eosinophil count of  $\geq$ 150 cells/µL or a fractional exhaled nitric oxide concentration of  $\geq$ 25 parts per billion (ppb). In OCS-dependent patients with severe asthma, dupilumab significantly reduced the need for OCS by ~70% while at the same time reducing asthma exacerbations and improving FEV1 compared to placebo.

Type 2 inflammation plays a critical role in the pathogenesis of ABPA. The hypothesis that blocking key mediators of type 2 inflammation will lead to clinical benefit in patients with ABPA is supported by a post-hoc subgroup analysis from the completed dupilumab phase 3 pivotal study EFC13579 (QUEST) in patients with moderate-to-severe asthma who met the suggested criteria for ABPA diagnosis at baseline. The results from a total of 30 patients (n=18 in the combined dupilumab group and 12 in the combined placebo group) provide compelling clinical evidence for the efficacy of dupilumab in patients with ABPA. Dupilumab treatment compared to placebo showed an approximately 80% reduction in annualized severe exacerbation events and a 0.26L improvement in change from baseline to week 24 in pre-bronchodilator (BD) FEV1. In clinical practice, serum total IgE, which is elevated in patients with ABPA, is monitored to assess ABPA disease activity. Dupilumab suppressed serum total IgE by approximately 70% from baseline over a 52-week treatment period. Overall, dupilumab was well tolerated in this subgroup of patients with ABPA.

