#### 9.1.1. Footnotes for the Schedule of Events Table

#### Footnotes for Table 1 Schedule of Events

\*Visits 5, 7, 9, and 10 will be performed as phone visits for patients not receiving OCS at baseline. For patients receiving OCS at baseline, these visits should be performed in-clinic if the patient remains on OCS on the day of the clinic visit. If OCS has been discontinued, these visits can be either in-clinic or performed as a phone visit at the discretion of the investigator. Assessments/procedures marked with an asterisk should only be performed if the visit occurs in-clinic.

\*\*After the last patient has completed visit 14/week 24 of the treatment period or withdrawn from the study, all patients still currently in the treatment period (between visit 15/week 26 and visit 27/week 50) should return to the clinic 2 weeks from their last dose/treatment administration to complete their EOT visit and all its applicable assessments. For patients who have withdrawn from the study treatment but remain in the study, the EOT visit will take place 2 weeks from their last visit. All patients must have their EOS visit 12 weeks after their EOT visit.

- a. Prior to screening, patients must be on a stable background therapy for asthma which may include ICS in combination with a second controller medication (eg, LABA, LTRA, theophylline, etc) for at least 3 months with a stable dose ≥1 month prior to baseline. Patients requiring a third controller are allowed to participate in this study. The third controller should also be used for at least 3 months with a stable dose ≥1 month prior to visit 1. Patients requiring systemic steroids of up to 10 mg per day (or up to 30 mg every alternate day) as controller medication are permitted.
- b. Randomization/baseline visit is defined as day 1. The visit schedule should be adhered to within  $\pm 1$  week for the screening period,  $\pm 3$  days for the randomized IMP treatment period, and  $\pm 7$  days for the post-IMP treatment period.
- c. All assessments at visit 2 (day 1) are to be conducted pre-IMP dose except for the assessment of local tolerability of SC injections.

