The annualized rate of severe respiratory exacerbations requiring either hospitalization or observation for >24 hours in an ED/urgent care facility over the 24-52-week treatment period is also a secondary efficacy endpoint.

For each of the aforementioned respiratory exacerbation efficacy endpoints, severe respiratory exacerbations will be determined based on the information entered in the Adverse Event eCRF. Specifically, adverse event records with verbatim term that includes the text “severe respiratory exacerbation” will be selected for analysis. To determine whether a severe respiratory exacerbation is ABPA-related, the date/time of each severe respiratory exacerbation event recorded on the Adverse Event eCRF will be used to identify the prior and subsequent serum total IgE measurements. To determine, whether a severe respiratory exacerbation event required hospitalization or observation for >24 hours in an ED/urgent care facility, the information entered in the “Comment” field on the Adverse Event eCRF will be used; sites will enter the text “HEDURG: Yes” into the comment field to indicate severe respiratory exacerbations requiring hospitalization or observation for >24 hours in an ED/urgent care facility, as instructed in the Clinical Completion Guidelines (CCGs).

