10.3. Vital Signs

The following vital signs parameters will be recorded and summarized according to the Schedule of Time and Events in Section 14.2:

- Systolic blood pressure
- Diastolic blood pressure
- Pulse rate
- Body temperature
- Respiratory rate
- Weight

Vital signs values and change from baseline in vital signs values at all scheduled post-baseline assessment time points will be summarized via descriptive statistics by treatment group.

For summaries of body temperature, all measurements will be converted to oral equivalent. If the method of temperature collection is not available, the measurement will not be eligible for inclusion in the summary. Measurements will be converted to oral equivalent as follows:

- axillary temperature + 0.3°C = oral equivalent temperature
- rectal temperature – 0.5°C = oral equivalent temperature
- ear temperature – 0.5°C = oral equivalent temperature

Vital signs measurements will be evaluated by PCSV criteria, specifically identifying patients with at least 1 post-baseline measurement that meets the PCSV criteria (see Section 14.3). Patients meeting the PCSV criteria will be summarized by patient count (and percentage) for a post-baseline PCSV measurement by treatment group.

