11.4. Unscheduled Assessments and Assignment of Data to Visit Windows

Unscheduled Assessments

The determination of values for by-visit analyses for both efficacy and safety variables will be based on assessments available from scheduled visits, or from unscheduled visits if the scheduled visit was not performed.

Extra assessments (e.g., laboratory data or vital signs associated with non-protocol-specified visits or obtained in the course of investigating or managing AEs) will be included in data listings, but not in summaries except for the endpoint determination. If more than one laboratory value is available for a given visit, the first observation will be used in summaries.

Assignment of Data to Visit Windows

Data analyzed by visit (including efficacy, laboratory, vital signs, ECG, ADA, etc.) will be summarized by the study scheduled visits described in the Schedule of Time and Events in Appendix 14.2.

The analysis visit windows are created per the Schedule of Time and Events for each parameter and will only be applied if the data from the study scheduled visits are unavailable. The following general, hierarchical rules will be applied for mapping the unscheduled visits and/or the early termination visit, EOT visit, or EOS visit (which will subsequently be collectively referred to as the “early termination of treatment or study” [ETTS] visit) for each parameter.

Note that the EOT visit is coded as “Week 52/ Visit 28” for all patients, regardless of the variable 24-52-week treatment period.

1. If the ETTS visit falls in an analysis window which already has an observed value of the parameter from the scheduled visit, the ETTS visit will be mapped to the next scheduled visit, provided there is no observed value of the parameter at the next scheduled visit.
2. If there is no observed value of the parameter from the scheduled visit and if both the ETTS visit and 1 or more unscheduled visits of the parameter are available in the same analysis visit window, only the ETTS visit may be mapped to a scheduled visit.
 - a. Note: If at least 2 of the EOT, EOS, and early termination visits are available in the same analysis visit window, then the ETTS visit to be mapped to the scheduled visit will be selected in the following hierarchical order: EOT visit, EOS visit, early termination visit.

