- q. Hematology will include hemoglobin, hematocrit, platelet count, total white blood cell (WBC) count, differential count, and total red blood cell (RBC) count.
- r. Hematology will include hemoglobin, hematocrit, platelet count, total white blood cell count, differential count, and total red blood cell count.
- s. Urinalysis will include specific gravity, pH, glucose, ketones, blood, protein, nitrate, leukocyte esterase, urobilinogen, and bilirubin. If any parameter on the dipstick is abnormal, a urine sample should be sent to the central laboratory for quantitative measurement. If positive for protein and/or red blood cells, microscopic analysis will be performed by the central laboratory.
- t. Serum pregnancy test will be conducted at visit 1 and urine dipstick pregnancy tests will be conducted at other visits. A negative result must be obtained at visits 1 and 2 prior to randomization.
- u. Pharmacokinetic (PK) and ADA samples are to be collected prior to the administration of the drug. In the event of suspected serious adverse events (SAEs), such as anaphylaxis or hypersensitivity, additional samples for the analysis of ADA and dupilumab drug concentration may be collected as close to the event as practically possible.
- v. Exhaled nitric oxide assessment is conducted prior to spirometry and following a fast of ≥ 1 hour.

- w. If the patient experiences an exacerbation, an unscheduled visit is to be performed for the collection of an additional blood sample for serum total IgE at the time of, or as soon as possible after, the exacerbation.
- x. If collection is not completed at randomization, sample can be taken at a following visit. To be collected prior to IMP administration
- y. Blood samples will be collected at selected sites. Only patients who are not on chronic systemic corticosteroids and not on oral antifungal therapy at baseline will be allowed to participate in the blood immunophenotyping substudy.
- z. Unscheduled visits may be necessary to repeat testing following abnormal laboratory results, for follow-up of AEs, or for any other reason as warranted. If the patient develops a respiratory exacerbation, he/she will be required to have an unscheduled visit as soon as possible, and a blood sample for serum total IgE needs to be collected.

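### Laboratory PCSV tables count unscheduled values, so the arm with more exacerbations has its hematology tested more often; the effect is probably small, but the plan has no scheduled-visit table to check it against

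*SAP*

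**What the plan says.** **Counting rule.** SAP 10.2 counts patients with at least one post-baseline laboratory value meeting the criterion and reports number and percentage by treatment group, with no allowance for how often each patient was tested. It adds: "All measurements collected during the study, including values from unscheduled visits, will be used in the PCSV analyses". SAP 1.4 provides for one set of PCSV tables per safety category.

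**What triggers an unscheduled visit.** Footnote z of SAP 14.2 says: "If the patient develops a respiratory exacerbation, he/she will be required to have an unscheduled visit as soon as possible". Protocol 9.2.2.3 says the same for all respiratory exacerbations. In the schedule, the Unscheduled Visit column marks vital signs, physical examination, hematology and serum total IgE. Blood chemistry, urinalysis and ECG are not marked there. The footnotes (w and z) name only the total IgE sample.

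**Expected difference in exacerbations.** Protocol 3.3.1, reporting a post-hoc subgroup of 18 dupilumab and 12 placebo patients, says: "Dupilumab treatment compared to placebo showed an approximately 80% reduction in annualized severe exacerbation events".

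**Vital signs.** SAP 10.3 says: "Vital signs measurements will be evaluated by PCSV criteria, specifically identifying patients with at least 1 post-baseline measurement that meets the PCSV criteria". It does not say whether unscheduled values count.

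**General rule.** SAP 11.4 says that extra assessments, including laboratory data or vital signs obtained while investigating or managing AEs, "will be included in data listings, but not in summaries except for the endpoint determination". Exacerbations are AE records: under SAP 7.1.2, "severe respiratory exacerbations will be determined based on the information entered in the Adverse Event eCRF".

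**The concern.** A proportion of patients with at least one flagged value rises with the number of values examined. Here, part of that number depends on an outcome that treatment is expected to change. If dupilumab prevents exacerbations, its patients have fewer unscheduled hematology draws, and fewer draws taken during acute illness, than placebo patients. The hematology PCSV percentages by arm then differ even if the drug has no effect on blood counts, and the difference favours dupilumab. With about 30 patients per arm, one or two extra flagged placebo patients could hide a modest real excess on dupilumab.

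The by-visit laboratory summaries use scheduled time points but do not count PCSVs, so the legible plan offers nothing to separate the two explanations. SAP 10.2 and 11.4 also give different instructions for values obtained while managing an AE, and two programmers could build different vital-sign tables.

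**Working it through.** The documents give no figure for this effect, so there is nothing to reproduce. The question is how large the artefact could be.

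**Inputs from the documents**
- Scheduled post-baseline hematology: Weeks 4, 8, 12, 24, 36, 44, EOT and EOS. That is m = 8 draws over 52 weeks of treatment, and m = 5 if treatment ends at Week 24 (Weeks 4, 8, 12, EOT, EOS).
- Dupilumab exacerbation rate = 0.2 × placebo (the 80% reduction in Protocol 3.3.1).
- About 30 patients per arm (Protocol 7.1).

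**Assumptions**
- Placebo rate λ = 0.24 to 2 per year. No placebo rate is stated. Protocol section 1 says exacerbations occur in up to 24% to 50% of patients each year, which motivates the lower end only.
- PCSV risk p = 2% per scheduled draw in both arms, and no drug effect.
- One hematology draw per exacerbation, with PCSV risk q.
- Draws independent, exacerbations Poisson, follow-up exacerbations ignored.
- Middle case: m = 6.75 draws over T = 38/52 = 0.731 years.

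**Formula**

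P(at least one PCSV) = 1 − (1 − p)^m × exp(−λ·T·q)

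**Scheduled draws only (middle case).** 1 − 0.98^6.75 = 12.7% in both arms, a gap of 0.

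**Extra testing alone, q = p = 2% (middle case)**

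| λ per year, placebo | Draws, placebo vs dupilumab | PCSV, placebo vs dupilumab | Gap (points) | Patients of 30 |
|---|---|---|---|---|
| 0.24 | 6.93 vs 6.79 | 13.0% vs 12.8% | 0.2 | 0.07 |
| 0.5 | 7.12 vs 6.82 | 13.4% vs 12.9% | 0.5 | 0.15 |
| 1 | 7.48 vs 6.90 | 14.0% vs 13.0% | 1.0 | 0.30 |
| 2 | 8.21 vs 7.04 | 15.3% vs 13.3% | 2.0 | 0.60 |

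Worked line for λ = 1: placebo 1 − 0.8725 × exp(−0.731 × 0.02) = 14.0%; dupilumab 1 − 0.8725 × exp(−0.146 × 0.02) = 13.0%.

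With 24 weeks for everyone (m = 5) the gap runs from 0.2 to 1.3 points; with 52 weeks (m = 8), from 0.3 to 2.7. At 52 weeks with p = q = 5% and λ = 2 it reaches 5.0 points, or 1.5 patients of 30.

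**If exacerbation samples are more often abnormal, q = 10%.** At λ = 1 in the middle case: placebo 1 − 0.8725 × exp(−0.731 × 0.10) = 18.9%, dupilumab 14.0%, a gap of 4.9 points. Allowing patients to differ in exacerbation rate (gamma-Poisson, dispersion 1) gives 18.7% vs 14.0%. The documents give no source for a 10% risk.

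**Direction.** With no drug effect, the all-values table moves only one way: whichever arm has more exacerbations gains flagged patients.

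**The case against.** The strongest reply is that counting every value is the inclusive choice for safety, that PCSV tables are descriptive with no between-arm test, and that the effect is minor. Much of this stands.

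- **Hematology at the exacerbation visit rests on a shared column.** That column also serves repeat laboratory tests and AE follow-up, while the text on exacerbation visits asks only for total IgE. One draw per exacerbation is a fair reading of the schedule, not a certainty.
- **A reader might infer that PCSV rates in general will favour dupilumab.** The documents do not support that: chemistry (including ALT and AST), urinalysis and ECG are not marked at unscheduled visits.
- **A reader might infer that the vital-sign table is biased in the same way.** This is not established. SAP 10.3 lacks the sentence on unscheduled values, and 11.4 would keep values obtained while managing AEs out. There is a related imbalance for patients on OCS at baseline: at Weeks 6, 10, 14 and 16 "these visits should be performed in-clinic if the patient remains on OCS on the day of the clinic visit", but after OCS stops the visit may still be in clinic at the investigator's discretion.
- **Eosinophils are a poor example of values pushed up.** Systemic steroids given for an exacerbation make the direction uncertain. The criterion also requires a baseline at or below 0.5 Giga/L or ULN, in a population where more than 500 cells/µL is a supportive entry criterion. Symptomatic eosinophilia is reviewed separately as an adjudicated AESI.
- **Large gaps need an assumed higher risk at exacerbation.** Part of that excess is real abnormality from illness or its treatment.

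What the reply does not remove is that the hematology count depends on exacerbation frequency, that no scheduled-visit PCSV count stands beside it, and that 10.2 and 11.4 disagree.

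**Conclusion.** The point holds for hematology and is modest. If placebo has more exacerbations, its hematology PCSV percentages are pushed up relative to dupilumab by unequal testing. From extra testing alone the gap is about 0.2 to 2 percentage points, under one patient in 30, at a 2% risk per sample, 0.24 to 2 exacerbations per year on placebo, and an 80% reduction taken from a small post-hoc subgroup. It reaches about 5 points at one exacerbation per year only if exacerbation samples carry a 10% risk, and that figure would mix artefact with true abnormality. For vital signs the finding is an unclear rule, not a demonstrated bias. Chemistry, urinalysis and ECG are largely unaffected. It would go too far to conclude that the plan makes dupilumab look safer overall. The reconciliation of 10.2, 10.3 and 11.4 is needed whatever the size of the effect.

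**What to change.** - **SAP 10.2:** keep the all-values laboratory PCSV table. Add a hematology PCSV table by arm restricted to scheduled visits, to be read beside it, and show the number of measurements per arm.
- **SAP 11.4:** add a sentence saying how the extra-assessments rule relates to the PCSV analyses, so that it agrees with 10.2.
- **SAP 10.3:** state whether unscheduled vital signs count. If they do, add the same scheduled-visit table, leaving out Weeks 6, 10, 14 and 16 because those in-clinic visits are not common to all patients.
- **SAP 1.4:** adjust the single-set statement to allow the added tables.

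The cost is SAP wording and one or two descriptive tables from data already collected. The small downside is that a scheduled-only table omits abnormalities seen only during acute illness, which is why the all-values table stays.
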